Protocol

Cognitive Outcomes of Brain Stimulation As a Later in Life Treatment (COBALT): A Phase II Randomized Controlled Trial

Document History:

Version	Date	Author	Notes
0.1	February 27,2023	[name] & [name]	Original draft
0.2	April 6, 2023	[name] & [name]	Listed University of Texas at Dallas as an external site for administration of electroencephalography and some cognitive outcomes.
0.3	March 14, 2024	[name]	Review
0.4	March 14, 2024	[name] & [name]	Modified analysis plan as follows. Changed primary outcome analysis from mixed effects models to ANCOVA, with baseline performance as the covariate. Updated mixed effects models to be sensitivity analysis in plan. Added chi-square tests for evaluating significance of proportions of clinically meaningful change.
0.5	April 15, 2025	[name]	Revised recruitment strategy to include digital tools in electronic health record to screen eligible patients who opted to be contacted for research.
1	April 15, 2025	[name]	Location of research site at University of Texas at Dallas changed to correspond to the relocation of the lab for electroencephalography and some cognitive outcomes.

Version: Final

Signatures

Principal Investigators: [name], PhD and [name]

Sponsor: Texas Alzheimer's Research and Care Consortium

Title: Cognitive Outcomes of Brain Stimulation As a Later in Life Treatment (COBALT)

Trial registration: ClinicalTrials.gov; NCT05564715

Trial design: randomized, double-blind, parallel-group sham-controlled trial

Number of arms: 2

Trial site: 1) University of Texas Southwestern Medical Center
2) University of Texas at Dallas

Protocol ID: STU-2022-0799

Participant time in trial: Two months

Background:

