Participants with a clinical diagnosis of aMCI will be enrolled and randomized to receive 10 sessions of either 1mA HD-tDCS or sham stimulation. All participants will be stable on oral medications for a minimum of 1 month before initiation of study procedures. Each HD-tDCS session will be 20 minutes in duration and have electrodes configured to target the preSMA/dACC, consisting of a single anode at Fz (1 mA) and 4 cathodes (all at 0.25 mA) at FP1, FP2, F7, F8. EEG and neuropsychological tasks will be completed at baseline, immediate after session 10, and a 2-month follow-up. Participants randomized into the sham group will have the opportunity to return after 2 months for an open-label phase to receive active treatment while being unblinded to their condition group. For participants crossing over from sham-to-active treatment in the open-label phase, EEG and neuropsychological tests will be obtained again immediately following the 10 HD-tDCS sessions and at a 2-month follow-up. With this design, we expect a 15% attrition rate and plan on enrolling ~30 adults to achieve our completed sample of 24.

Below is a table summarizing the study visits. In Phase 1, participants will be randomized to active or sham stimulation and complete 12 visits. In Phase 2, participants in the sham group will be invited to receive the active condition as an open-label phase, which would involve 11 additional visits in the study.

SUMMARY OF VISITS		
Phase 1	PROCEDURES	TIME
Visit 1	Pre-testing neuropsychological assessment/semantic EEG	3 hours
Visits 2-10	HD-tDCS active or sham stimulation	30 minutes
Visit 11	HD-tDCS active or sham stimulation and post-testing neuropsychological assessment/semantic EEG	3 hours

Visit 12	8-week follow-up assessments/semantic EEG	3 hours
Phase 2	Open-label Phase	
Visits 13-21	HD-tDCS active stimulation (for Phase 1 sham group participants only)	30 minutes
Visit 22	HD-tDCS active stimulation and post-testing neuropsychological assessment/semantic EEG	3 hours
Visit 23	8-week follow-up assessments/semantic EEG	3 hours

Inclusion criteria:

1. Age 55 and older
2. Fluent in English
3. Active diagnosis of aMCI
4. Deficit in at least one measure of language functioning, defined as performing >1 standard deviation below the standardized score mean on either the Boston Naming Test, phonemic fluency, or semantic fluency measures

Exclusion criteria:

1. Substance use disorder within past year
2. Has metal fragments or implants in skull/head

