Arm 2: For the sham condition, parameters will consist of the current being ramped up over 60 seconds until it reaches 1 mA and then stopped. This allows for the same scalp sensation for both the sham and active condition so that subject and experimenter will remain blinded. This ramp up for one minute and then stopped and off for 20 minutes will be given each 20-minute sham session to keep the timing and subjective experience similar to the active condition.

All HD-tDCS protocols for participants will be pre-programmed into the Neuroelectrics software. HD-tDCS protocols will be set by a PI ([name]) for each participant using an encrypted approach, labeling with the participant research identifier to conceal condition assignment. Aside from the PI, other study team members will be unaware of the HD-tDCS condition allocation to preserve blinding.

Randomization: Participants will be randomized at a ratio of 1:1 to receive active 1 mA and sham conditions. Randomization of HD-tDCS condition assignments will be generated by a digital program, and the assignments (Protocol 1 = active or 2= sham) recorded in an encrypted spreadsheet that only the PI ([name]) has access to.

Blinding: Participants will be informed that sham and active HD-tDCS will be used in the study, but they will be blinded to condition. Aside from the PI ([name]), other study team members who deliver HD-tDCS and perform assessments will be blinded to HD-tDCS condition. Both the subject and study personnel will complete a questionnaire to check if blinding was successful.

Sample size calculation: Pre-study power analyses were conducted for the most power intensive phase (Phase 1 - randomized controlled trial) using a clinically relevant effect size derived from our prior studies. A sample size of 20 provides 80% power to detect a $f = .27$ effect size for the analysis of the primary outcome using an analysis of covariance model, assuming the baseline covariate of performance explains $R^2 = .2$ and $\alpha = .05$. Given that both our and other's research without intervention suggests that effect sizes tend to be larger in EEG compared to cognitive measures, we expect the effect size of EEG outcomes to be at least equivalent to cognitive outcomes.

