General linear models (analysis of covariance) will be used to evaluate whether cognitive performance following all HD-tDCS sessions statistically differs between HD-tDCS conditions, covarying for pre-treatment scores. Mixed effects models will be used to examine for a significant interaction between HD-tDCS condition and time across the 3 outcome intervals. Participants with missing time points will not be excluded. Clinically meaningful change associated with HD-tDCS will also be assessed. Proportions of individuals with a 5+ standardized score increase (T-score) on each measure of cognitive functioning will be characterized and evaluated using chi-square analyses. Statistical significance will be set at $\alpha = .05$.

EEG behavioral data will be tested using mixed effects models to examine for a significant interaction between HD-tDCS condition and time. Group assignment (active vs sham) will be used as the between subject factor; Time Point and Condition will be two within subject factors. In the Binding task, Condition included retrieval versus non-retrieval trials, while in the Association task, Condition included associated versus not-associated trials. Statistical significance will be corrected for the multiple electrode-time tests that will be performed using the Benjamini Hochberg false discovery rate.

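### The stated 80% power is wrong: the ANCOVA as specified has about 25% power at N = 20 and about 29% at the planned 24 completers

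*Combined protocol and SAP*

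**What the plan says.** The sample size paragraph (Procedures, Sample size calculation) makes one quantitative claim: "A sample size of 20 provides 80% power to detect a $f = .27$ effect size for the analysis of the primary outcome". It names analysis of covariance as the model, assumes that baseline performance explains R² = .2, and sets alpha at .05. It describes the effect size as clinically relevant and derived from the team's earlier studies. It also uses this effect size as a lower bound for the EEG outcomes.

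The Design section gives a different number of completers: "we expect a 15% attrition rate and plan on enrolling ~30 adults to achieve our completed sample of 24".

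The Statistical analysis section confirms the model: post-treatment score compared between conditions, adjusted for the pre-treatment score, at alpha .05. Sidedness is not stated anywhere. The Document History entry for version 0.4 records how this became the primary analysis: "Changed primary outcome analysis from mixed effects models to ANCOVA, with baseline performance as the covariate".

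**The concern.** An effect of f = .27 in two equal groups is a standardized difference of d = 0.54. Ten participants per arm cannot detect that with 80% power when the covariate removes only a fifth of the variance. The sentence gives every input needed to check it except sidedness, so it can be tested on its own terms.

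This is the only justification given for the size of the trial. If the figure is wrong, a reader of a non-significant result would wrongly believe that an effect of this size had an 80% chance of being detected, and could take the result as evidence against it. The expectation for the EEG outcomes leans on the same effect size.

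**Working it through.** **Inputs.** From the sample size paragraph: N = 20, f = .27, ANCOVA, R² = .2, alpha = .05. From Procedures: two arms, 1:1 allocation. From Design: 24 completers. Assumed: N = 20 is the total (the planned completed sample is 24 in total) and the test is two-sided.

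**Formula.** For two groups and one covariate, the F test has 1 and N − 3 degrees of freedom and noncentrality λ = N f² / (1 − R²). Here f² = .27² = .0729 and 1 − R² = .8.

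**The plan's own figure.**

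| N | λ | df | Power, noncentral F | Power, simulated (40,000 runs) |
|---|---|---|---|---|
| 20 | 20 × .0729 / .8 = 1.82 | 1, 17 | 24.7% | 23.6% |
| 24 | 24 × .0729 / .8 = 2.19 | 1, 21 | 29.2% | 28.5% |

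A normal approximation with d = 0.54 and residual SD √.8 gives 27.1% and 31.5%. The stated 80% is not reproduced.

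**Other readings that keep f = .27.**

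| Reading | N = 20 | N = 24 |
|---|---|---|
| f already adjusted for the covariate (λ = N f²) | 20.7% | 24.3% |
| One-sided test | 36.4% | 41.5% |
| R² of .04 (the .2 read as a correlation) | 21.4% | – |

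With 20 per arm (40 in total), power is 46.0% two-sided and 59.1% one-sided. With all 30 enrolled participants analysed it is 35.8%.

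**What would be needed for 80%** (two-sided):

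- With R² = .2, the detectable effect is f = 0.59 (d = 1.19) at N = 20 and f = 0.54 (d = 1.07) at N = 24.
- With f = .27 and R² = .2, 89 completers are needed, or 90 with equal arms. If f is already covariate-adjusted, the number is 110.
- With f = .27 kept and R² allowed to change, baseline would have to explain about 83.5% of the variance at N = 20 or about 80% at N = 24.

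**On the T-score scale.** This step assumes the normative SD of 10; the documents give no trial SD. Then f = .27 is 0.54 × 10 = 5.4 points, and the effect detectable with 24 completers is about 10.7 points. The residual SD is 10 × √.8 = 8.94. The standard error of the adjusted difference with 12 per arm is 8.94 × √(2/12) = 3.65. With t = 2.08 on 21 df, the expected 95% confidence interval half-width is 2.08 × 3.65 = 7.6 points.

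**Where the figure might come from (inference only).** Two readings outside the stated text land near 80%:

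- *.27 is f², and the test is one-sided.* Then f = √.27 = .52, λ = 20 × .27 / .8 = 6.75, and power at N = 20 is 80.2%. Two-sided, it is 68.8% at N = 20 and 77.5% at N = 24.
- *A group-by-time interaction over three visits,* with λ = f² × N × 3 / (1 − ρ). N = 24 and ρ = .5 give 80.7%; N = 20 gives 72.0% at ρ = .5 and 81.7% at ρ = .6. This would fit a value left over from the mixed-model plan that version 0.4 replaced, but the documents give no ρ.

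**The case against.** The strongest objection is that one ANCOVA reading does give 80% at N = 20: .27 as f² with a one-sided test. It uses every number in the sentence and needs no extra parameter. If that is what was done, the effect is f = .52 and two-sided power at 24 completers is 77.5%, close to target. The fault would then be a mislabelled metric and an unstated one-sided test, and the 25–29% would not describe the effect the team had in mind. The studies behind the effect size are not available to settle this.

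This stands as a caution about the cause. It does not rescue the sentence. The text says f, and no one-sided test is planned anywhere. Under this reading the sentence would misstate its effect size (d of about 1.04, not 0.54) and would still need correcting.

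Three smaller points are fair. The carry-over explanation depends on a correlation the documents do not give, so nothing should rest on it. Planning for 24 completers when the calculation uses 20 is not a contradiction in itself; it may be a margin, and 24 / 0.85 = 28.2 agrees with enrolling about 30. The 5-point T-score criterion in the Statistical analysis section concerns change in an individual, so its closeness to 5.4 points for a group difference is only a rough comparison.

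It can also be said that a phase II trial may properly be small. That is true, but the issue here is the power claimed, not the number enrolled.

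**Conclusion.** The concern holds and the sentence must be corrected. On its stated inputs, power is about 25% at N = 20 and about 29% at the planned 24 completers, against a claimed 80%. At 24 completers the chance of missing f = .27 is about 71%, where the plan implies 20%. The effect the trial can detect with 80% power is about twice the one stated.

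These figures assume a two-sided test, a total N, and .27 as Cohen's f before covariate adjustment. No change of sidedness, covariate convention or per-arm reading tried with f = .27 brings power at N = 20 or 24 above 42%, and even 20 per arm with a one-sided test gives 59.1%. Which element of the sentence is in error cannot be determined from the documents. That the elements do not fit together is certain. The T-score figures rest additionally on an SD of 10.

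**What to change.** Replace the power statement, leaving enrolment unchanged, with wording such as:

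> *With 24 completers, the ANCOVA (baseline R² = .2, two-sided alpha .05) has 80% power for f = 0.54 (d about 1.07) and about 29% power for f = .27.*

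This is correct arithmetic whatever the source of the error. In addition:

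- State the effect-size metric, sidedness and software. Recover the original calculation if it exists, so that the record shows which element was wrong.
- Base the calculation on the 24 planned completers, or say explicitly that 24 is a margin over 20.
- Commit to reporting the adjusted between-group difference with its 95% confidence interval, and to describing a non-significant result as inconclusive.
- If the change comes after data collection has begun, date it and label it a correction. Do not repeat the 80% figure uncorrected in the trial report.

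The cost is protocol wording only: no extra participants, visits or analyses. The stated power becomes less favourable.

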The pre-supplemental motor area (preSMA) and dorsal anterior cingulate cortex (dACC) have been shown to play a role in episodic memory and word retrieval. Although the hippocampus is a brain structure most often associated with early deficits in amnesic mild cognitive impairment (aMCI), the earliest clinical threshold preceding dementia, the dACC is another node in the neural network for episodic memory that may be more accessible to neurostimulation methods. Entraining the preSMA/dACC circuits with 10 sessions of neurostimulation could be used to improve cognitive functioning evaluated by EEG-based and neuropsychological measures. High-definition transcranial direct current stimulation (HD-tDCS) is one neurostimulation approach that uses an array of small electrodes to pass a low level current through targeted brain regions (e.g., anterior cingulate cortex) to modulate neuronal activity and brain circuitry.

Purpose:

The purpose of this study is to examine the efficacy of HD-tDCS to the preSMA/dACC region and its influence on EEG and neuropsychological measures in patients with aMCI.

Primary Objective:

[figure not shown]
- Determine if HD-tDCS enhances verbal episodic memory functioning in aMCI

Secondary Objective:

- Determine if HD-tDCS enhances word retrieval functioning (i.e., language) in aMCI
- Evaluate if cognitive changes produced from HD-tDCS persist for 2 months
- Evaluate if HD-tDCS modulates EEG-derived neural synchronizations associated with memory functions to inform potential target engagement

Design:

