Episodic memory functioning will be assessed through standardized scores in Total Learning and Delayed Recall for the Rey Auditory Verbal Learning Test (verbal memory).

Secondary

- Language will be assessed through standardized scores for the Boston Naming Test-Short Form, DKEFS Phonemic Fluency, and DKEFS Category Fluency.

Additional Outcomes

- Visual memory will be assessed through standardized scores in Total Learning and Delayed Recall for the BVMT-R.
- Attention will be assessed through standardized scores for the WAIS-IV Digit Span and DKEFS Visual Scanning.
- Processing speed will be assessed through standardized scores for the SWAPS, DKEFS Color Naming, DKEFS Word Reading, DKEFS Motor Speed, DKEFS, Number Sequencing, and DKEFS Letter Sequencing.
- Executive functions will be assessed through standardized scores for DKEFS Category Fluency Switching, DKEFS Inhibition, DKEFS Inhibition/Switching, and DKEFS Number-Letter Switching.
- Visuospatial organization will be assessed through standardized scores for the WAIS-IV Visual Puzzles.

Rey Auditory Verbal Learning Test (RAVLT). A 15-item list learning and memory task where the tester reads aloud a list of nouns. The RAVLT includes 5 learning trials, an interference trial, a delayed recall trial, and a yes/no delayed recognition trial. The tester records how many items the patient remembers over several repeated trials and then again for the interference and 30-minute delayed recall trial. The RAVLT is a direct measure of verbal episodic memory and has multiple alternate forms. The scores for Total Learning and Delayed Recall are the primary outcomes of interest.

Delis-Kaplan Executive Function System (DKEFS) Phonemic Fluency. This is an assessment of word retrieval during which the patient is required to produce as many words in one minute that begin with a specific letter (e.g., F, A, or S). The outcome measure for this task is the total number of correct responses across the trials.

DKEFS Semantic Fluency. This is an assessment of word retrieval that involves 3 conditions. The patient is required to produce as many words in one minute that are members of specific categories (e.g., condition 1 = *animals*, condition 2 = *boy's names*) or switching between two different categories

(condition 3 = fruits-and-furniture items). The outcome measures for this task are the total words named for the two semantic conditions and the total words named during the switching condition.

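### Two co-primary RAVLT scores are each tested at .05 with no rule for whether one or both must succeed; if either suffices, the false-positive rate of the primary conclusion is about 7–10%, not 5%

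*Combined protocol and SAP*

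**What the plan says.** All references are to the combined protocol and SAP.

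- **Primary Objective** lists one aim: "Determine if HD-tDCS enhances verbal episodic memory functioning in aMCI".
- **Cognitive Outcomes**, under Primary and again in the RAVLT description, attaches two scores to that aim: "The scores for Total Learning and Delayed Recall are the primary outcomes of interest".
- **Statistical analysis** gives the main test: "General linear models (analysis of covariance) will be used to evaluate whether cognitive performance following all HD-tDCS sessions statistically differs between HD-tDCS conditions", with the pre-treatment score as covariate. It then adds a condition-by-time test ("Mixed effects models will be used to examine for a significant interaction between HD-tDCS condition and time across the 3 outcome intervals") and chi-square tests on the proportion gaining 5 or more T-score points. One threshold covers these tests: "Statistical significance will be set at" α = .05.
- The only multiplicity adjustment in that section is for EEG: "Statistical significance will be corrected for the multiple electrode-time tests that will be performed using the Benjamini Hochberg false discovery rate".
- **Sample size calculation** refers to the primary outcome in the singular and powers one ANCOVA at α = .05.
- **Document History**, version 0.4, records that ANCOVA became the primary analysis and that the mixed models became a sensitivity analysis. The Statistical analysis section does not repeat that label.

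**The concern.** The plan is sized as one test at 5% but specifies two. It contains no composite, no ordering of the two scores, no split of alpha and no statement of what counts as success. A significant difference on Total Learning alone, or on Delayed Recall alone, could therefore be reported as meeting the single primary objective.

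With 24 expected completers, one significant score out of two is a plausible result. A reader could not then tell whether the trial had met its objective, and a rule chosen after seeing the results would not protect the error rate. The authors correct for multiplicity in the EEG data, but nothing comparable covers the primary outcome.

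**Working it through.** **Inputs from the document.** Two primary scores; α = .05 for each; 1:1 allocation; 24 planned completers, so 12 per arm. The test is read as two-sided because the section asks whether performance "statistically differs between HD-tDCS conditions, covarying for pre-treatment scores"; sidedness is not stated outright.

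**Assumed input.** ρ, the correlation between the two test statistics, which is roughly the between-score correlation after baseline adjustment. The documents do not give it, so I show 0 to .9.

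**The plan's own figure.** No family-wise error rate is stated. The only related figure is 80% power at N = 20, f = .27, R² = .2, α = .05 for one ANCOVA. The noncentrality is λ = N f²/(1 − R²) = 20 × .0729/.8 = 1.82 on 1 and 17 df. This gives 24.7%, so the stated power does not reproduce. That is a separate matter; here it shows only that the calculation assumes one test at .05.

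**Error rates when neither score is truly affected** (bivariate normal, critical value 1.96):

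- Either score significant: 1 − P(|Z₁| ≤ 1.96 and |Z₂| ≤ 1.96). At ρ = 0 this is 1 − .95² = .0975.
- Either score significant in favour of active: 1 − P(Z₁ ≤ 1.96 and Z₂ ≤ 1.96). At ρ = 0 this is 1 − .975² = .0494.
- Both significant: .05 + .05 − P(either). At ρ = 0 this is .0025.

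| ρ | Either, two-sided | Either, false benefit | Both required |
|---|---|---|---|
| 0 | 9.75% | 4.94% | 0.25% |
| .5 | 9.07% | 4.54% | 0.93% |
| .6 | 8.75% | 4.38% | 1.25% |
| .7 | 8.35% | 4.17% | 1.65% |
| .8 | 7.81% | 3.90% | 2.19% |
| .9 | 7.04% | 3.52% | 2.96% |

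The comparators for a single test are 5% two-sided and 2.5% for false benefit. Simulated ANCOVAs with 12 per arm agree to within about 0.3 percentage points (9.2–9.3% at ρ = .5, 8.0–8.1% at ρ = .8). The last column assumes no effect on either score. If one score truly changes and the other does not, the both-required rule can approach 5% but not exceed it.

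**After adjustment.** Holm's first step tests the smaller p-value at .025. When neither score is affected, the family-wise error is then 4.0–4.7% for ρ from .8 down to .5, and it stays at or below 5% for any correlation.

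**Cost of adjustment.** Simulated with 12 per arm and d = 2f = .54, in units of the unadjusted SD. The correlation between baseline and post-treatment (retest) is assumed.

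| Setting | Any score significant, unadjusted | Any score significant, Holm | Mean of the two T-scores |
|---|---|---|---|
| Effect on both, ρ = .7, retest .45 | 0.39–0.40 | 0.28 | 0.32 |
| Effect on both, ρ .5–.8, retest .45–.8 | 0.37–0.71 | 0.26–0.59 | 0.31–0.66 |
| Effect on one only, ρ .5–.8, retest .45 | about 0.31 | 0.20–0.21 | 0.11–0.13 |

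**The case against.** The strongest objection is that with no success rule the error rate is undetermined, not inflated. If the authors meant both scores to succeed, no adjustment is needed. That stands as a limit on the claim: 7–10% is conditional on an either-score reading that the plan does not state, and on a correlation it does not give. It does not remove the gap, because the plan does not adopt the both-scores rule either and leaves the choice open until the results are known.

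A second objection is that α = .05 is a threshold for each test, not a promised family-wise rate, and that the objective concerns benefit, so the relevant error is smaller. This is fair, and the false-benefit column is there for that reason. The relative inflation remains: 3.5–4.9% against 2.5%.

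A reader might go further and count the mixed-model and chi-square tests on both scores as additional routes to the primary claim, which would give a considerably higher error rate. The documents do not support that. The Document History calls the mixed models a sensitivity analysis, and a three-visit interaction also fits the secondary objective on persistence. The responder proportions are introduced as an added assessment. No section lets either kind of test establish the primary claim, and the figure would also depend on an unspecified continuity correction.

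A reader might also total the uncorrected tests over all the cognitive scores. The other 18 scores are already tiered as secondary or additional, so that total does not bear on the primary conclusion.

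**Conclusion.** The gap is real: two primary scores, one objective, an uncorrected .05 for each, and no rule for combining them. If either score suffices, the two-sided false-positive rate of the primary conclusion is about 7–10% for between-score correlations from .9 down to 0, and the chance of a false claim of benefit is about 3.5–4.9% against 2.5%. If both were required, the rate would not exceed 5%. The calculation rests on two-sided tests, normal scores, complete data and an assumed correlation. It would be wrong to say that the plan's error rate simply is some figure above 5%, because that needs a success rule the plan has not set. This should be fixed; it does not undermine the design.

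**What to change.** In the Statistical analysis section:

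1. State that the primary claim rests on the two RAVLT ANCOVAs after session 10, tested with Holm: the smaller p-value at .025 and, only if that is significant, the other at .05. Say which score or scores a positive claim then covers.
2. Carry over from the Document History that the mixed models are a sensitivity analysis, and add that the responder chi-square tests are supportive. Neither can establish the primary claim.
3. Date the change before any comparison of the arms on RAVLT. Sham participants who enter the open-label phase are unblinded individually, so participant-level unblinding is not a usable cut-off.

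The change needs no new data or visits. Its cost is a lower chance of at least one significant score: about 0.28 instead of 0.39–0.40 with d = .54 on both scores, 12 per arm, between-score correlation .7 and retest correlation .45. Over correlations .5–.8 and retest .45–.8 it is roughly 0.26–0.59 instead of 0.37–0.71.

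The mean of the two T-scores, tested alone at .05, is not an equivalent substitute. It does slightly better than Holm when both scores move (0.32 against 0.28 in the same setting). If only one score moves, its power at retest .45 falls to about 0.11–0.13, against 0.20–0.21 for Holm. Requiring both scores would also control the error without adjustment, but it is harder to meet (power about 0.17 in the same setting with both scores affected).

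### The 2-month persistence objective has no 2-month contrast: the three-visit interaction is as likely to be significant for a vanished effect as for a lasting one

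*Combined protocol and SAP*

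**What the plan says.** The Secondary Objective list includes this aim: "Evaluate if cognitive changes produced from HD-tDCS persist for 2 months". The Design section sets the visits that could inform it: "EEG and neuropsychological tasks will be completed at baseline, immediate after session 10, and a 2-month follow-up".

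For the cognitive outcomes, the Statistical analysis section gives three analyses:

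- An analysis of covariance to "evaluate whether cognitive performance following all HD-tDCS sessions statistically differs between HD-tDCS conditions, covarying for pre-treatment scores". It does not say which visit or visits this covers.
- A mixed model over all three visits: "Mixed effects models will be used to examine for a significant interaction between HD-tDCS condition and time across the 3 outcome intervals". The section adds "Participants with missing time points will not be excluded". It does not say how time is coded.
- A responder analysis: "Proportions of individuals with a 5+ standardized score increase (T-score) on each measure of cognitive functioning will be characterized", compared by chi-square. Again no visit is named.

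The section names no active-versus-sham comparison at 2 months, no 2-month estimate with a confidence interval, and no rule for concluding that an effect has persisted. The EEG behavioral data get a model of the same kind: "EEG behavioral data will be tested using mixed effects models to examine for a significant interaction between HD-tDCS condition and time".

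**The concern.** Persistence is a statement about one visit: is there still a difference between the arms at 2 months? A condition-by-time interaction over three visits answers another question, namely whether the difference between the arms changes at any point from baseline onward. An effect present only right after session 10 satisfies it, and so does an effect that is fully retained.

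If the interaction is the evidence for the durability objective, a significant result could be reported as persistence when nothing remains at 2 months. This visit matters particularly because sham participants may move to open-label active treatment after it. It is therefore the last randomized comparison in the trial.

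**Working it through.** **Inputs from the protocol.** The Sample size calculation gives N = 20, f = .27, baseline R² = .2 and α = .05. Randomization is 1:1. The Design section gives a completed sample of 24. For two equal groups, d = 2f = 0.54. The baseline-to-post correlation implied by R² is √.2 ≈ .45.

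**Assumptions, because the plan is silent.** Time is categorical, SDs are equal, the correlation ρ between any two visits is the same (compound symmetry), data are complete, and α is two-sided. I also show ρ from .2 to .8 and an effect of d = 1.0. Neither that range nor d = 1.0 comes from the documents.

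**The plan's own figure.** The stated 80% power for the ANCOVA does not follow from its inputs. With λ = N f²/(1 − R²) = 20 × 0.0729/0.8 = 1.82 on 1 and 17 df, power is 24.7%. With N = 24, λ = 2.19 on 1 and 21 df gives 29.2%. That is a separate issue, but the same formula gives the power of a 2-month ANCOVA below.

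**The interaction test.** With n per arm and between-arm differences d_t at the three visits,

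λ = (n/2) × Σ(d_t − mean d)² / (1 − ρ), on 2 and 2(2n − 2) df.

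- Vanished effect (0, d, 0): the mean is d/3 and the sum of squares is d²(1/9 + 4/9 + 1/9) = 2d²/3.
- Persistent effect (0, d, d): the mean is 2d/3 and the sum of squares is d²(4/9 + 1/9 + 1/9) = 2d²/3.

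Both give λ = n d²/[3(1 − ρ)]. The test has identical power for the two patterns at every d, n and ρ.

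**Numbers.** For N = 20, λ = 10 × 0.2916/(3 × 0.553) = 1.76. For N = 24, λ = 12 × 0.2916/(3 × 0.553) = 2.11. The 2-month ANCOVA column uses λ = N(d/2)²/(1 − ρ²) on 1 and N − 3 df.

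| N | d | ρ | Interaction significant, effect vanished | Interaction significant, effect persistent | 2-month ANCOVA significant, effect persistent |
|---|---|---|---|---|---|
| 20 | 0.54 | .45 | 19% | 19% | 25% |
| 24 | 0.54 | .45 | 22% | 22% | 29% |
| 24 | 0.54 | .7 | 38% | 38% | 42% |
| 24 | 1.0 (assumed) | .45 | 64% | 64% | 74% |
| 24 | 1.0 (assumed) | .7 | about 90% | about 90% | about 90% |

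At d = 0.54, over ρ from .2 to .8, the interaction is significant in 14% to 46% of trials with N = 20 and in 17% to 54% with N = 24, for either pattern.

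**Simulation check.** With 20,000 trials at N = 24, d = 0.54 and ρ = .45, the interaction was significant in 22.5% (vanished) and 22.4% (persistent). An unstructured multivariate version gave 20.8% and 21.0%. A 2-month between-arm contrast was significant in 4.9% when the effect had vanished. Simulated power for the 2-month ANCOVA is one to two percentage points below the formula values in the table.

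**The case against.** **The ANCOVA may already cover 2 months.** Two assessments follow the last session, and the wording does not limit the ANCOVA to the first. This stands in part: if both visits were meant, one clause naming them would supply most of what is missing. As written, the 2-month visit is not named, and nothing links any analysis to the persistence objective.

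**Visit-by-visit means are routinely examined after an interaction, and no passage says that a significant interaction will be read as persistence.** Both are true. The planned model can produce the right contrast, so the gap lies in the specified test and not in the model. Leaving the contrast unnamed, however, leaves the choice until after the data are seen.

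**A reader might infer that the interaction will usually be significant even when the effect has gone.** The documents do not support this. At the protocol's effect size and R² the figure is 19% to 22%. At ρ = .45 it passes one half only if d is at least 0.95 (N = 20) or 0.86 (N = 24), well above 0.54.

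**A reader might also infer that the direct contrast would be well powered, or clearly more powerful.** It would not. Its power at the protocol's effect size is about 25% to 29%. Its advantage is modest at ρ = .45 and small to negligible at .7 and above. The case for it is that it answers the question.

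**Scope.** The interaction is the only stated three-visit test for the cognitive outcomes. The EEG behavioral model is a second interaction, with the same limitation.

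**Conclusion.** The concern holds in this form: the persistence objective has no test that can answer it. Under the stated assumptions, the three-visit interaction has the same chance of significance for a vanished as for a fully persistent effect: about 19% (N = 20) to 22% (N = 24) at the protocol's inputs. At an assumed d = 1.0 with 12 per arm, the chance rises to 64% (ρ = .45) or 90% (ρ = .7), again for both patterns.

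The exact equality rests on categorical time and compound symmetry. With another correlation structure the two probabilities need not match, but a post-only effect would still drive the 2-df test. If time were entered as a linear trend, the arithmetic would differ, and the plan does not say. This should be corrected before analysis. It is a wrong choice of test for one secondary objective and does not affect the primary comparison.

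**What to change.** In the Statistical analysis section:

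1. Define the persistence test as the baseline-adjusted active-minus-sham difference at the 2-month visit, with its 95% confidence interval. Take it as a named contrast from the mixed model already planned, or run the same ANCOVA on the 2-month score. The mixed-model route fits better with the statement that participants with missing time points are kept, because an ANCOVA on the 2-month score needs that score to be observed.
2. Base any claim of persistence on that contrast, and keep the omnibus interaction as descriptive.
3. Name the visit or visits to which the ANCOVA and the chi-square analysis apply, and state that time is categorical in the mixed model.
4. State that the contrast has only about 25% (N = 20) to 29% (N = 24) power at the protocol's effect size, so a non-significant result will not be read as loss of effect.

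The cost is a few sentences and one contrast per outcome. No new data or visits are needed. The drawback is low power, which the interaction shares.
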